2.4 Section 6.5 Rescue criteria

If the pre-breakfast SMPG values taken on three consecutive days or if any of the FPG samples analysed by the central laboratory exceeds the limit of:

- 15.0 mmol/L (270 mg/dL) from after baseline to week 6
- 13.3 mmol/L (240 mg/dL) from week 7 to week 12
- 11.1 mmol/L (200 mg/dL) from week 13 to week 26

and if no treatable intercurrent cause for the hyperglycaemia has been identified, the subject should be called for a confirmatory FPG measurement as soon as possible. The FPG sample should be analysed by the central laboratory and if it exceeds the limits described above, the subject must discontinue treatment with trial product.

2.5 **Section 8.1.3 Screening failures**

If a screened subject for any reason is not eligible for the trial or are not randomised within 14 ealendar days after the screening visit (V1), the subject will be considered a screening failure. For screening failures the screening failure form in the eCRF must be completed with the reason for not continuing in the trial. Serious and non-serious AEs from screening failures must be transcribed by the investigator into the eCRF. Follow-up of SAEs must be carried out according to section 12.3. Screening failures experiencing an AE that would otherwise qualify for adjudication (see section 12.7) will not be adjudicated as no trial product has been administered.

2.6 Section 8.1.4 Randomisation (V2)

Randomisation must NOT take place more than 14 calendar days after V1 (screening). All results from screening assessments, including laboratory results, ECG and eye examination must be available and reviewed by the investigator and the inclusion/exclusion criteria must be carefully reviewed to ensure the subject is eligible prior to the randomisation.

2.7 Section 8.1.7 Premature discontinuation of trial product

Once the two follow-up contacts after discontinuation of trial product are completed the subject should be contacted by phone every 4 weeks. Information on antidiabetic medication and information on potential major cardiovascular events (MACE) and any SAEs occurring since last contact must be collected and recorded in the eCRF. Phone contacts must be documented in the medical record and in the eCRF. The subject should finally come in for a V32A at week 26 to report MACE, SAEs, total daily insulin dose, use of other antidiabetic medication, and have fasting body weight measured and a blood sample taken to measure HbA_{1c}, see flow chart (section 2).

Protocol Amendment 2 Trial ID: NN9068-4229 UTN:U1111-1168-9343

EudraCT No.: 2015-001596-48

CONFIDENTIAL

Date: Version: Status: Page:

28 November 2016 | Novo Nordisk Final 12 of 19

2.8 **Section 8.2 Laboratory assessments**

All samples will be destroyed on an ongoing basis after the analysis or at the latest at the completion of the clinical trial report (CTR). However in case of abnormal haematology analysis test results, part of the sample may be kept for up to 2 years.

2.9 **Section 8.4.1 Body measurements**

Height is measured without shoes in centimetres (cm) or inches. and rounded to the nearest em or inch.

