To compare the effect and safety of IDegLira versus IGlar after 26 weeks.

Key secondary endpoints

The key secondary endpoints are:

- Change from baseline in body weight after 26 weeks
- Number of treatment-emergent severe or BG confirmed symptomatic hypoglycaemic episodes during 26 weeks
- Insulin dose, total daily dose (U) after 26 weeks
- Responder after 26 weeks (Yes/No) for $HbA_{1c} < 7.0\%$
- Change from baseline after 26 weeks in fasting plasma glucose (FPG)
- Number of treatment-emergent adverse events during 26 weeks

Trial design:

This is a 26-week randomised, active-controlled, multicentre, multinational, two-arm parallel, open-label, treat-to-target trial (TTT) in subjects with T2DM. Subjects inadequately controlled on OAD

Protocol
Trial ID: NN9068-4229
UTN: U1111-1168-9343

Date: 20 November 2015 Version: 2.0 Status: Final

Page:

9 of 107

treatment with SGLT2i will be eligible for the trial. Pre-trial OAD treatments must include SGLT2i either as monotherapy, or in combinations with metformin \pm dipeptidyl peptidase-4 inhibitor (DPP4i) \pm pioglitazone. If a subject is treated with DPP4i these have to be discontinued at randomisation. Subjects on fixed dose combinations of SGLT2i and DPP4i should be shifted to the corresponding SGLT2i, whereas fixed dose combinations of SGLT2i and metformin should be continued. Pioglitazone is allowed in all subjects, except those treated with dapagliflozin. The trial will compare IDegLira to IGlar as an add-on to treatment with SGLT2i \pm OAD. Inadequately controlled T2DM is defined as an HbA_{1c} level of 7.0-11.0%, both inclusive.

Trial population:

Planned number of subjects to be randomised and started on trial products is 416.

Key inclusion criteria

EudraCT No.: 2015-001596-48

- Male or female, age ≥ 18 years at the time of signing informed consent
- Subjects diagnosed (clinically) with type 2 diabetes mellitus
- HbA_{1c} 7.0-11.0% [53-97 mmol/mol] (both inclusive) by central laboratory analysis
- Body mass index (BMI) $\geq 20 \text{ kg/m}^2 \text{ and } < 40 \text{ kg/m}^2$
- Insulin naïve subjects; however short term insulin treatment for a maximum of 14 days prior to the day of screening is allowed, as well as prior insulin treatment for gestational diabetes
- A stable daily dose for at least 90 days prior to the day of screening of any SGLT2i in monotherapy or in combination with metformin ± DPP4i ± pioglitazone. Use of pioglitazone is not allowed in subjects treated with dapagliflozin

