4.2.2.2 Supportive secondary endpoints

Supportive secondary efficacy endpoints:

- Responder after 26 weeks (Yes/No) for:
 - $HbA_{1c} < 7.0\% *$

 Protocol
 Date:
 20 November 2015
 Novo Nordisk

 Trial ID: NN9068-4229
 Version:
 2.0

 UTN: U1111-1168-9343
 Status:
 Final

Page:

19 of 107

 \circ HbA_{1c} < 7.0% without weight gain

- o HbA_{1c} < 7.0% without treatment-emergent severe or BG confirmed symptomatic hypoglycaemic episodes during the last 12 weeks of treatment
- \circ HbA_{1c} < 7.0% without treatment-emergent severe or BG confirmed symptomatic hypoglycaemic episodes during the last 12 weeks of treatment and without weight gain
- \circ HbA_{1c} \leq 6.5%

EudraCT No.: 2015-001596-48

- o HbA_{1c} \leq 6.5% without weight gain
- O HbA_{1c} \leq 6.5% without treatment-emergent severe or BG confirmed symptomatic hypoglycaemic episodes during the last 12 weeks of treatment
- \circ HbA_{1c} \leq 6.5% without treatment-emergent severe or BG confirmed symptomatic hypoglycaemic episodes during the last 12 weeks of treatment and without weight gain
- Change from baseline after 26 weeks in:
 - Waist circumference
 - Fasting plasma glucose (FPG)*
- Fasting lipid profile
 - Cholesterol
 - o Low-density lipoprotein cholesterol (LDL cholesterol)
 - High-density lipoprotein cholesterol (HDL cholesterol)
 - o Very-low-density lipoprotein cholesterol (VLDL cholesterol)
 - o Triglycerides
 - o Free fatty acids
- Self-measured plasma glucose (SMPG) 9-point profile
 - o 9-point profile
 - Mean of the 9-point profile
 - Prandial plasma glucose increments (from before meal to 90 min after breakfast, lunch and dinner). The mean increment over all meals will be derived as the mean of all available meal increments
- Vital signs
 - Systolic and diastolic blood pressure

Supportive secondary safety endpoints:

- Number of treatment-emergent adverse events during 26 weeks*
- Number of treatment-emergent nocturnal severe or BG confirmed symptomatic hypoglycaemic episodes during 26 weeks
- Number of treatment-emergent hypoglycaemic episodes according to ADA definition during 26 weeks
- Change from baseline in clinical evaluation after 26 weeks:
 - o Electrocardiogram (ECG)

- Eye examination
- o Physical examination
- o Pulse rate
- Change from baseline in laboratory assessments after 26 weeks:
 - o Biochemistry
 - o Haematology
 - o Calcitonin
 - Urine albumin/creatinine ratio

Supportive secondary health economics endpoints:

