Unless otherwise specified, all continuous measurements will be summarised descriptively at each visit by treatment using on-treatment observed data. Endpoints are summarised by arithmetic mean, standard deviation (SD), median, and minimum and maximum value. Selected endpoints, e.g. endpoints that are analysed log-transformed, will be reported with geometric mean and coefficient of variation in place of mean and SD. For measurements over time, mean values will be plotted to explore the trajectory over time. Observed data will be used as the basis for plotting data if not otherwise specified. For endpoints that are summarised with geometric mean, the geometric mean values will be plotted. Mean profiles for the primary and continuous confirmatory secondary endpoints by time of treatment discontinuation and treatment will be plotted in order to investigate discontinuation patterns. In addition, selected endpoints will be summarised by empirical distribution, box and mean change from baseline over time plots.

The primary objective is to confirm the effect of IDegLira in terms of glycaemic control in subjects with T2DM on previous treatment with SGLT2i ± OAD therapy. The primary estimand for the primary objective will be the difference in change from baseline in HbA_{1c} after 26 weeks between T2DM subjects randomised to IDegLira and IGlar, both in combination with SGLT2i ± OAD, regardless of whether subjects remained on initially assigned treatment or not until week 26. This estimand is a de facto estimand addressing effectiveness. With the aim of comparing treatment strategies this estimand is considered clinically relevant. It resembles the ITT principle. For the confirmatory secondary endpoints de facto estimands addressing effectiveness are chosen as primary estimand too.

The secondary estimand for the primary objective will be the difference in change from baseline in HbA_{1c} after 26 weeks between T2DM subjects randomised to IDegLira and IGlar, both in combination with SGLT2i ± OAD, attributable to randomised treatment, if all randomised subjects had tolerated and adhered to treatment until week 26. This estimand is a de jure estimand addressing efficacy. In the non-inferiority setting this estimand has higher assay sensitivity than an effectiveness estimand. The estimand is considered clinically relevant since it provides information to treating clinicians about the glycaemic efficacy attributable to IDegLira for the purpose of

CONFIDENTIAL

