17.4.2 Supportive secondary endpoints

The supportive secondary endpoints will be addressed in terms of the primary estimand only.

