Responder for HbA_{1c} without treatment-emergent severe or BG confirmed symptomatic hypoglycaemic episodes and weight gain after 26 weeks will be defined as

- HbA_{1c} < 7.0%without treatment-emergent severe or BG confirmed symptomatic during the last 12 weeks of treatment, and change in body weight from baseline \leq 0 kg
- HbA $_{1c} \le 6.5\%$ without treatment-emergent severe or BG confirmed symptomatic during the last 12 weeks of treatment, and change in body weight from baseline ≤ 0 kg

Theses endpoints will be analysed as the composite HbA_{1c} and weight responder endpoints, where subjects with less than 12 weeks of treatment conservatively will be set to being non-responder.

Waist circumference change from baseline after 26 weeks

Change from baseline in waist circumference will be analysed by multiple imputation J2R.

Fasting plasma glucose change from baseline after 26 weeks

Change from baseline in FPG will be analysed by multiple imputation J2R.

CONFIDENTIAL

Date: Version: Status: Page:

20 November 2015 | Novo Nordisk 2.0 Final 82 of 107

Fasting lipid profile after 26 weeks

Cholesterol, LDL cholesterol, HDL cholesterol, VLDL cholesterol, triglycerides and free fatty acids will be analysed separately by multiple imputation J2R. In these statistical analyses, the endpoint will be log-transformed and so will the corresponding baseline covariate.

Self-measured plasma glucose (SMPG) 9-point profile change from baseline after 26 weeks

The following six endpoints from the 9-point SMPG profile will be defined:

- 9-point profile (individual SMPG values). [One endpoint]
- Mean of the 9-point profile, defined as the area under the profile (calculated using the trapezoidal method) divided by the measurement time. [One endpoint]
- Prandial plasma glucose increments (from before meal to 90 min after meal for breakfast, lunch and dinner). The mean increment over all meals will be derived as the mean of all available meal increments. [Four endpoints]

A linear mixed effect model will be fitted to the 9-point SMPG profile data. The model will include treatment, pre-trial OAD, time (within 9-point profile), the interaction between treatment and time, the interaction between pre-trial OAD and time as fixed factors, and subject as random effect. From the model mean profile by treatment and relevant treatment differences will be estimated and explored.

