1.1 Rationale for the amendment

This amendment has been prepared in order to:

- 1. Update List of abbreviations
- 2. Update the flowchart:
 - deletion of footnote 7 as not applicable in final eCRF
 - update of flowchart and protocol section 8.17 to specify that subjects who premature discontinue trial product should attend V32A in a fasting state
- 3. Clarify the rescue criteria in section 6.5 in order to make it clear that they apply after baseline visit meaning after initiation of treatment
- 4. Update the wording relating to randomisation visit timeframe in section 8.1.3 in order to add an element of flexibility which may be required to accommodate scenarios where an eligible subject is not able to attend for randomisation on day 14 due to force majeure
- 5. Delete the wording relating to randomisation visit timeframe in section 8.1.4 as this is specified in Section 2 Flowchart
- 6. In section 8.2 add that in case of abnormal haematology analysis test results, part of the sample may be kept for up to 2 years
- 7. In section 8.4.1 Height, deletion of text regarding rounding to nearest cm or inch as not applicable in final eCRF
- 8. In section 8.5.2 insert ">" in front of 3.9 mmol/L. In addition, in the 5th bullet in order to align with the diary, specify that date, time, and dose of last anti-diabetic treatment should not be collected in connection with a hypoglycaemic event between V32 and V33
- 9. In section 8.5.5 update text in order to specify that the ECG should be repeated in case the randomisation takes place more than 14 days after the ECG is obtained. In addition delete whom the ECG should be obtained by
- 10. In section 8.6.1, align with the PRO questionnaire that site staff can fill in the headings on the questionnaire forms and review the questionnaire for empty fields and potential adverse events
- 11. In Summary and section 9.1 specify that SGLT2i and metformin not necessarily "will be" but "can be" reimbursed in accordance with local legislation and Ethics Committee approval
- 12. In section 12.1 update serious adverse event with current protocol template text and definition of Major Adverse Cardiovascular Events (MACE)
- 13. In section 12.2 specify that "fasting body weight" should be measured at V32A

- 14. In section 12.5.1 specify forms to be completed
- 15. Update made to section 13.2 in order to align with other parts of the protocol

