2.16 Section 12.2 Reporting of adverse events

All events meeting the definition of an AE must be collected and reported. This includes events from the first trial-related activity after the subject has signed the informed consent until the end of the two post-treatment follow-up periods. Please be aware that hypoglycaemic episodes should not be reported before any trial drug is given e.g. hypoglycaemic episodes should be reported from the randomisation visit (V2). Subjects discontinuing trial product prematurely (see section 6.4) will be contacted every 4th week and asked for information about antidiabetic medication, MACE and SAEs. These subjects should finally come in for a V32A at week 26, only to assess antidiabetic medication, MACE, SAEs, fasting body weight and a blood sample to measure HbA_{1c}.

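### FPG is assigned only the de facto estimand but is not measured at the fasting week-26 visit V32A, so the week-26 FPG of every IDegLira discontinuer is imputed from an IGlar-only model

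*Protocol*

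**What the plan says.** **Status of FPG.** The Summary lists change in FPG among the key secondary endpoints. Section 4.2.2.2 classes it as supportive and stars it for public disclosure. It is not in the test hierarchy of section 17.4.1.

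**Estimand.** Section 17.4.2: "The supportive secondary endpoints will be addressed in terms of the primary estimand only". For HbA1c, section 17 defines the primary estimand as the difference between arms "regardless of whether subjects remained on initially assigned treatment or not until week 26", and calls it a de facto estimand.

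**Analysis.** Protocol version 2.0, section 17.4.2.1: "Change from baseline in FPG will be analysed by multiple imputation J2R". Amendment 2 (section 2.24) renames the method unconditional multiple imputation; the steps in section 17.3.1 stay the same.

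**Data after discontinuation.** Amendment 2 (section 1.1) states that "subjects who premature discontinue trial product should attend V32A in a fasting state". As amended, section 8.1.7 has these subjects report events, insulin dose and other antidiabetic medication at V32A, "have fasting body weight measured and a blood sample taken to measure" HbA1c. As amended, section 12.2 words the list as closed: "These subjects should finally come in for a V32A at week 26, only to assess antidiabetic medication", then MACE, SAEs, fasting body weight and HbA1c. In the amended flow chart HbA1c and body weight are marked at V32A; the FPG row stops at V32.

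**The concern.** The estimand asks what FPG is at week 26 in everyone randomised, including those who stopped. For those who stopped, the plan never measures that quantity, although they come to the site at week 26, fasting, and give blood. The off-treatment part of the FPG effect therefore comes from an assumption that the trial's data cannot check. A sample that is not taken cannot be recovered later in the analysis, so the point belongs in the protocol.

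What is at stake is how far a disclosed supportive result reflects its stated estimand.

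**Working it through.** **1. The plan's own figure.** Section 6.1 gives 416 randomised and 354 expected to complete on trial product. Section 17.1 anticipates 15% discontinuation. 416 × (1 − 0.15) = 353.6, which rounds to 354, so the figure is reproduced. Expected discontinuers: 416 − 354 = 62, or 31 per arm.

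**2. FPG available for a discontinuer.**
- Values from planned visits before stopping.
- One value at the end-of-treatment visit corresponding to V32, which section 8.1.7 places soon after stopping. It falls near week 26 only for late stoppers.
- No value at V32A.

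**3. What the imputation does with them.** In section 17.3.1, step 1 sets to missing all post-randomisation values of discontinued IDegLira subjects who lack V32A data. With FPG substituted for HbA1c, as is done for body weight, this covers every IDegLira discontinuer, and the end-of-treatment FPG goes too. Steps 3 to 5 fit the imputation model to IGlar subjects plus IDegLira subjects with retrieved data. For FPG the second group is empty, so the model is IGlar only. Step 1 does not apply to IGlar subjects, whose earlier values are kept.

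**4. Effect on the estimate.** Let D_on be the difference in subjects who stay on treatment and D_off the true week-26 difference between discontinuers in the two arms, with 15% in each arm.
- Estimand: 0.85 × D_on + 0.15 × D_off.
- Estimate: about 0.85 × D_on + 0.15 × 0, since discontinuers in both arms are filled from one IGlar model.
- Error (estimate minus estimand): about −0.15 × D_off.

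This is approximate, because IGlar discontinuers are imputed using their earlier values and IDegLira discontinuers from baseline. The documents give no D_off, so a range is assumed:

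| Assumed D_off (mmol/L) | Error (mmol/L) |
|---|---|
| −1.0 | +0.150 |
| −0.5 | +0.075 |
| 0 | 0 |
| +0.5 | −0.075 |
| +1.0 | −0.150 |

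**5. Simulation check.** Simplified one-visit model with 208 per arm, 15% discontinuation, 300 replicates and 10 imputations. Assumed: D_on = −0.5 mmol/L, baseline and residual SD 2. Monte Carlo error is about 0.01.

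| D_off | Truth | Estimate, no retrieval | Estimate, 70% retrieval |
|---|---|---|---|
| 0 | −0.425 | −0.414 | −0.424 |
| +1 | −0.275 | −0.408 | −0.334 |
| −1 | −0.575 | −0.412 | −0.540 |

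Without retrieved FPG the estimate stays near −0.41 while the truth moves by 0.30. With 70% retrieval it moves towards the truth but does not fully reach it.

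**6. What measuring at V32A would recover.** Attendance is not given, so a range is assumed:

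| Discontinuers with V32A FPG | Observed | Still imputed | Share of FAS imputed |
|---|---|---|---|
| 0% (as written) | 0 | 62 | 15.0% |
| 30% | 19 | 43 | 10.5% |
| 50% | 31 | 31 | 7.5% |
| 70% | 43 | 19 | 4.5% |
| 90% | 56 | 6 | 1.5% |

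**The case against.** The strongest reply is that this is a consistent scoping decision. Section 17 ties retrieved data to the confirmatory analyses, and V32A collects exactly the measurements those need: HbA1c, body weight and insulin dose. Amendment 2 puts retrieved data in the titles of the continuous confirmatory analyses and not in the FPG line. Waist, lipids, SMPG profile, blood pressure, pulse and the questionnaires are handled like FPG. Pulling towards the comparator is also what a reference-based method intends, and the error is zero if the true off-treatment difference is zero.

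Much of this stands. There is no contradiction: section 17 says that endpoints will also be assessed in subjects who discontinue, but it does not promise every endpoint at V32A. The decision still leaves FPG with one estimand and no week-26 data for the subjects who distinguish that estimand from an on-treatment one.

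Several stronger readings do not hold:
- **That discontinuers have no off-treatment FPG at all.** They are due one at the early end-of-treatment visit. What is missing is a week-26 value, and in the IDegLira arm the early value is then discarded.
- **That all 62 could be recovered.** Section 6.6 defines withdrawn subjects as those who decline further contact; they will not attend V32A. The documents do not split withdrawal from discontinuation with follow-up.
- **That glucose could be read from the HbA1c sample.** Section 8.2 leaves sampling supplies and handling to a laboratory manual that is not available here.
- **That HbA1c and body weight are free of the problem.** IDegLira discontinuers without V32A data get the same deletion and reference-based imputation for those endpoints. The difference is one of degree.
- **That the FPG result leans towards one arm.** The sign of the error follows D_off, which is unknown.

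**Conclusion.** The point holds as a low-cost improvement, not as an error in the plan. FPG is addressed only under the de facto estimand, yet the week-26 FPG of every IDegLira discontinuer comes from an IGlar-only model. Up to about 62 of 416 subjects (15%) are affected across the two arms. The estimate is about 0.85 times the on-treatment effect, and its error is 0.15 times the true off-treatment difference. That is at most 0.15 mmol/L if the difference lies within 1 mmol/L either way.

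This rests on 15% discontinuation in each arm, on step 1 being applied to FPG as it is to body weight, and on discontinuers in the two arms receiving similar imputed means. The off-treatment difference, the on-treatment effect, the SD and V32A attendance are assumptions. FPG lies outside the hierarchy, so the primary conclusion, the confirmatory tests and the Type I error do not change.

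**What to change.** Mark FPG in the V32A column of the flow chart. Add it beside HbA1c in the V32A lists of sections 8.1.7 and 12.2. State in section 17.4.2.1 that V32A FPG enters the FPG analysis as retrieved data, as for HbA1c. Step 1 then spares IDegLira discontinuers who have a V32A value, and the imputation model draws on them as well as on IGlar.

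The cost is one more central-laboratory assay for each discontinuer who attends (62 at most), possibly a separate glucose tube at the same draw, and matching document edits. The visit, the fasting requirement and the blood draw are already in place. Subjects without V32A FPG would still be imputed.
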